
I). At the end of this scan, the subject will be provided a brief (~5 to 10 min) break to relax out of the scanner.

J). Subjects will then be administered 1 mg/kg of intravenous hydrocortisone as a bolus over 90 seconds. Following this, subjects will be monitored by the investigative team for subjective and objective adverse events (see monitoring listed below).

K). A second low-dose CT scan and [C-11]NOP-1A scan will be acquired a minimum of 3.5-hours post hydrocortisone, identical to the methods outlined previously. The timing of the second [C-11]NOP-1A administration and subsequent PET scanning (i.e., ~ 3.5 to 4.5 hours) is based on previous basic science studies that have documented CRF-NOP interactions (Ciccocioppo et al., 2014a; Rodi et al., 2008). The proposed timing will also ensure that the maximum increase in amygdala cortisol and CRF ($T_{max} \sim 25$ to 30 min) following intravenous hydrocortisone (1mg/kg) has occurred prior to the PET scan (Cook, 2002).

Blood Sampling during [C-11]NOP-1A PET scans: Periodic arterial blood sampling will be performed during the PET studies for the quantitative data analyses (i.e. measurement of the radiotracer and its metabolites in the blood). These blood draws will not exceed 130 ml (about 9 tablespoonfuls) of blood in total. For each PET scans, hand-drawn arterial blood samples (0.5 ml) will be collected throughout the scan with no more than 20 collected during the first 2 min and no more than 15 collected at intervals of increasing duration minutes (no more than 35 total samples). Also, larger blood samples (3-5 ml) will be obtained at no more than 8 times during each PET scan for the determination of radiolabeled metabolites and protein binding. This would amount to no more than 43 arterial samples and a blood volume loss of no more than 60 ml (4-5 tablespoonfuls)/scan ($60 * 2 \text{ scans} = 120 \text{ mL}$). In addition to this two 3-5 mL blood samples will be drawn for measuring cortisol plasma levels for each post-hydrocortisone scan ($2 * 5 * 1 \text{ scan} = 10 \text{ mL}$). The timing of these cortisol blood samples will be $t=0$ and 1h post-hydrocortisone

L). Following this scan, all subjects will receive:

1. Physical Exam.
2. Mental Status Exam.
3. EKG.
4. Vital Signs measurement.

M). The subject will be evaluated by a physician to ensure they meet the following discharge criteria:

1. a blood pressure of $> 90/60$ and $< 150/90$.
2. a heart rate > 50 or < 110 .

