3. no reported subjective or objective side effects from the hydrocortisone at discharge.
4. a normal EKG (or not clinically significant, or no change from baseline EKG as determined by a physician)
5. a normal physical exam.
6. a normal mental status exam.

N). Healthy control who meet the above listed criteria following the PET scans will be

discharged home.

SUBJECT MONITORING:

A). Subject monitoring prior to the PET Scan

1. A physician will review screening labs, EKG and medical evaluation (see attached) prior to scan day.
2. Baseline review of systems and medication history (to document no change from screening).
3. Vital signs.
4. Urine toxicology screen.
5. A statement of use of a method of contraception for all subjects in the past 15 days (abstinence, barrier methods, oral contraceptive medications, etc.).
6. All female subjects of child bearing potential will undergo urine pregnancy testing to rule out pregnancy on the day of the PET scans prior to any of the PET scanning procedures.

B). Subject monitoring during PET scans

1. An experienced technician will be in both visual and verbal contact with the participant at all times during the study. If the participant voices any difficulty or desires to be removed from the scanner, or if the technician sees any indication that the participant is experiencing discomfort, the participant will be immediately removed from the scanner and verbally reassured.

C). Subject monitoring on hydrocortisone

1. The hydrocortisone will be administered by a physician investigator familiar with the protocol. The physician investigator will also be available in the PET facility to monitor the subject on hydrocortisone.
2. Blood pressure and heart rate will be recorded once prior to hydrocortisone and following hydrocortisone every ten minutes for the first 60 minutes, then every 15 minutes thereafter (up to at least 120 min).
3. Subjects will be assessed once at baseline (time 0), once at 60 minutes post-hydrocortisone (t=60 min), and once before the second [C-11]NOP scan with visual analog scales such as the PSS, HAM-A and CES D (scales attached in 2.8) to evaluate their subjective feelings while on hydrocortisone.

2.6.1

Will blood samples be obtained as part of this research study?

* Yes

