	Other Risks:	Since this is a single-site, open study with a relatively small number of subjects, the data and safety monitoring plan will be implemented using close monitoring of individual subjects by a single individual (the PI). The PI or co-investigators are in daily contact with the research staff who test the participants, score and enter the data and will monitor their procedures to ensure that confidentiality is maintained. We will do everything in our power to protect confidentiality. Information gathered as part of the study including all research records in locked files, and the identity of all specimens and medical information by a research record number, rather than by the subject's name or social security number.
View	Research Activity:	Risk of Hydrocortisone
	Common Risks:	Headache, nausea, vomiting, dizziness, insomnia, restlessness, depression, anxiety, unusual moods, increased sweating, increased hair growth, reddened face, thinned skin, easy bruising, tiny purple spots, and irregular menstrual periods. Typically, these side effects are not bothersome and are reversible with time.
	Infrequent Risks:	Other rare, but serious adverse events reported in "medically ill individuals" include anaphylaxis, bradycardia, cardiac arrest, dermatitis, decreased carbohydrate and glucose tolerance, fluid retention, abdominal distention, bowel/bladder dysfunction, negative nitrogen balance, aseptic necrosis of femoral and humeral heads, convulsions, emotional instability, exophthalmoses, glaucoma.
	Other Risks:	It is also possible that hydrocortisone may interfere with the intended effects of vaccination or can increase their risk when exposed to fungal or viral infections.
	Research Activity:	Risk of Lidocaine

View	Common Risks:	The use of Lidocaine may result in mild reactions, including a metallic taste, ringing in the ear.
	Infrequent Risks:	Allergic reaction, which may include shortness of breath, itching, rashes, etc.
	Other Risks:	No Value Entered
View	Research Activity:	Risk of Lorazepam
	Common Risks:	Sedation.
	Infrequent Risks:	Dizziness, weakness, unsteady gait.
	Other Risks:	Serious allergic reaction, which may include rash, itching, swelling, severe dizziness, trouble breathing.
View	Research Activity:	Risk of MRI

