During and after the hydrocortisone administration, subjects will be under constant monitoring for serious adverse events (including anaphylaxis, bradycardia, etc.). Administration of hydrocortisone will take place in the presence of a physician. A twelve lead EKG, a code cart, and defibrillator are available in the room in case of complications. If there is a drop in blood pressure, IV fluids will be used to control the blood pressure response. In case of chest pain, chest tightness or other symptoms suggestive of cardiac ischemia, the experiment will be canceled and a twelve lead EKG will be immediately obtained to rule out angina (ST segment elevation or depression as compared to the baseline EKG) or arrhythmia. If serious medical signs and symptoms persist > 10 minutes, the subjects will be taken to the UPMC Presbyterian ER for further medical treatment. If psychiatric signs and symptoms persist > 10 minutes (example, depression, anxiety, etc.), the subjects will be managed by the PI (starting with re-assurance, and if need oral lorazepam 1-2 may be administered). If these symptoms persist and are a cause for a concern then a referral will be made to a higher level of care, example WPIC psychiatric emergency room. All subjects who receive hydrocortisone will be monitored for a minimum of 6 hours in the PET facility, following hydrocortisone administration. Subjects will be evaluated by a physician and discharged home only if they meet the following criteria: (a) a blood pressure of > 90/60 and < 150/90 (b) a heart rate > 50 or < 110 (c) no reported subjective or objective side effects from the hydrocortisone at discharge (d) a normal EKG (or not clinically significant, or no change from baseline as determined by a physician) (e) a normal physical exam (f) and a normal mental status exam.

5.2

What steps will be taken in the event that a clinically significant, unexpected disease or condition is identified during the conduct of the study?

* **Addressed below:**

If a clinically significant, unexpected disease or condition occurs during the conduct of the study that is directly related to study intervention, it will be evaluated and managed by one the physician investigators. If this event is an emergency, the subject will be taken to the UPMC Presbyterian ER and medical care will be initiated as needed.

5.3

All the risk questions (screening, intervention/interaction, follow-up) have been merged into one question (5.1).

[\[reviewer notes-\]](#)

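### The heart-rate discharge criterion joins its two limits with *or*, so every heart rate meets it and the item holds no one back

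*Combined protocol and SAP*

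**What the plan says.** Two places in the combined protocol and SAP set the discharge rule.

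- **2.6 step M:** "The subject will be evaluated by a physician to ensure they meet the following discharge criteria". The second item on the list is "a heart rate > 50 or < 110".
- **5.1.1, Risk of Hydrocortisone:** discharge is allowed only if the listed criteria are met. Items (a) and (b) read "a blood pressure of > 90/60 and < 150/90 (b) a heart rate > 50 or < 110".

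The readings come from step L, after the second scan, which includes "Vital Signs measurement". The other items on the list are "no reported subjective or objective side effects from the hydrocortisone at discharge", "a normal EKG (or not clinically significant, or no change from baseline EKG as determined by a physician", a normal physical exam and a normal mental status exam.

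5.1.1 also has a cancel rule, which stops the study for a blood pressure below 90/60 or above 150/90. It has no heart-rate counterpart.

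Under the infrequent risks of hydrocortisone, 5.1 lists rare serious events reported in medically ill people, which "include anaphylaxis, bradycardia, cardiac arrest" among others. 5.1.1 names bradycardia again as an event to watch for during and after dosing.

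**The concern.** A discharge criterion is a pass rule: it states what must be true before the subject leaves. For a pass rule to describe a range, both limits must hold together. Joined by *or*, a lower limit of 50 and an upper limit of 110 cover the whole scale, and the item becomes a formality.

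What is at stake is a safety check on healthy volunteers who have no prospect of direct benefit (5.12). The next planned contact after discharge is a telephone call about 1 to 7 days after the last scan (2.7). The heart-rate schedule under Subject Monitoring in 2.6 sets no action threshold, and the cancel rule covers blood pressure only. The discharge item is therefore the only place in the text provided where a heart-rate number could stop anything, and as worded it cannot. Discharging someone at 45 or 125 bpm would comply with this item, so an audit could not record it as a deviation from it.

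**Working it through.** The plan gives no calculated figure on this point, so there is none to reproduce. The check is one of logic.

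**Inputs**

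- Lower limit 50 bpm and upper limit 110 bpm, joined by *or* (2.6 step M and 5.1.1(b), same wording).
- Comparator: the blood-pressure item in the same two lists, with limits joined by *and*.
- Timing: second scan at least 3.5 hours after hydrocortisone (2.6 step K), 70 minutes of acquisition (2.6 step H).
- Monitoring: heart rate every 10 minutes for 60 minutes, then every 15 minutes to at least 120 minutes (2.6, Subject Monitoring, C).

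**As written.** The rule passes a rate if HR > 50 or HR < 110. To fail, a rate would have to be both ≤ 50 and ≥ 110, which is impossible. Testing each whole number from 0 to 300 gives 0 failures out of 301.

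**With *and*.** The rule passes a rate if HR > 50 and HR < 110. In whole beats that is 51 to 109, or 109 − 51 + 1 = 59 values. The other 301 − 59 = 242 values fail.

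| Heart rate | > 50? | < 110? | With *or* | With *and* |
|---|---|---|---|---|
| 45 bpm | no | yes | passes | held |
| 80 bpm | yes | yes | passes | passes |
| 125 bpm | yes | no | passes | held |

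**Which reading was meant.** Three rules can be set side by side:

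1. Blood pressure at discharge is a pass rule and uses *and*. This is correct.
2. Blood pressure in the cancel rule is a stop rule and uses *or*. This is correct.
3. Heart rate at discharge is a pass rule but uses *or*. This is the connective of a stop rule.

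The third is out of line with both of the others. Since the wording is identical in two sections, an error in reading the PDF is not a plausible explanation.

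**When the item applies.** The step L readings come no earlier than 3 h 30 min + 1 h 10 min = 4 h 40 min after the dose. The scheduled checks give at least 6 (10 to 60 minutes) + 4 (75 to 120 minutes) = 10 post-dose readings, and the required schedule may end at 2 hours. The wrist band covers the subject until both scans are complete.

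**The case against.** The strongest reply is that the slip changes little in practice, and most of that reply stands.

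- Heart rate is closely watched. A wrist band records it continuously until both scans are done (2.6 step F). There are at least ten scheduled post-dose readings, with a physician investigator in the facility (2.6, Subject Monitoring, C). Subjects stay at least 6 hours after the dose, and serious signs lasting more than 10 minutes lead to transfer to the emergency room (5.1.1).
- The discharge items apply jointly. A subject at 45 or 125 bpm must still pass a physician's evaluation, the side-effect item, the EKG item and a physical exam.
- A physician would very likely read the item as a range.
- A literal *and* could hold a healthy person whose usual resting rate is 50 or lower.

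The last point is right and shapes the fix. The others limit the impact but do not repair the wording: none of those safeguards carries a heart-rate number, and the item was presumably written so that discharge would not rest on judgement alone.

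A reader might infer more than this in two ways. One is that the discharge check as a whole fails. It does not; one item of six has no effect. The other is that someone with a cardiac history could be enrolled and then meet this loose rule, because 3.14(5) reaches only severe illness. The documents do not support that either. 5.1.1 excludes any history of cardiovascular disease, arrhythmia or an abnormal EKG; both sections bind, so the stricter one applies.

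**Conclusion.** The point holds as a minor but certain drafting error in a participant-safety rule. As written, the heart-rate item rejects no value. As evidently intended, it would pass 51 to 109 bpm and hold back rates of 50 or lower and 110 or higher. It applies to each of the up to 20 subjects who undergo the procedures.

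The documents give no distribution of heart rates, so the number of subjects outside 51 to 109 at discharge cannot be computed, and no harm is claimed. The reading of intent rests on the neighbouring blood-pressure item and on the cancel rule. The statement that no other numeric heart-rate limit exists is confined to the text provided. The primary outcome (percentage change in VT), its analysis and the power calculation do not depend on this item.

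**What to change.** In both 2.6 step M and 5.1.1(b), state the criterion as: *a heart rate > 50 and < 110, or no clinically significant change from baseline as determined by a physician*. The second clause follows the EKG item and covers a subject with a normally low resting rate. It would help to say that baseline means the reading taken just before hydrocortisone, which 2.6 (Subject Monitoring, C) already requires.

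The cost is one wording change in two places and no new measurement. An occasional subject may be held longer for physician review; the documents give no figure for how often.

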For projects not supported by a federal grant, upload the research plan that was submitted for funding:

Name Modified Date

If **Industry** support, provide the sponsor information and level of support:

If **Foundation** support, provide the sponsor information:

If **Other** support, provide the support information and level of support:

[\[reviewer notes-\]](#)

7.3

Is this study funded in part or whole by a PHS Agency?

* Yes

Does any investigator* involved in this study (select all that apply):

Name
 A. Have a financial interest (aggregated value of equity and remuneration** during the past or next twelve months) in a publicly-traded entity that either sponsors*** this research or owns the technology being evaluated or developed that exceeds \$5,000 but not \$10,000?
 B. Have a financial interest (aggregated value of equity and remuneration during the past or next twelve months) in a publicly-traded entity that either sponsors this research or owns the technology being evaluated or developed that exceeds \$10,000?
 C. Receive remuneration (during the past or next twelve months) from a non-publicly traded entity that either sponsors this research or owns the technology being evaluated or developed that exceeds \$5,000 but not \$10,000?
 D. Receive remuneration (during the past or next twelve months) from a non-publicly traded entity that either sponsors this research or owns the technology being evaluated or developed that exceeds \$10,000?
 E. Have equity in a non-publicly traded entity that either sponsors this research or owns the technology being evaluated or developed?
 F. Receive reimbursement or sponsorship of travel expenses (for one trip or a series of trips during the past or next twelve months) by an outside entity that either sponsors this research or owns the technology being evaluated or developed that exceeds \$5,000?
 G. Have rights as either the author or inventor of intellectual property being evaluated or developed in this research that is the subject of an issued patent or has been optioned or licensed to an entity?
 H. Have an officer or management position**** with a Licensed Start-up Company overseen by the COI Committee that either sponsors this research or owns the technology being evaluated or developed?
 I. Receive compensation of any amount when the value of the compensation would be affected by the outcome of this research, such as compensation that is explicitly greater

- for a favorable outcome than for an unfavorable outcome or compensation in the form of an equity interest in the entity that either sponsors this research or owns the technology being evaluated or developed?
-
- None of the above options apply and there are no other financial conflicts of interest in the conduct of this research.**

***Investigator** means the PI, co-investigators, and any other member of the study team, regardless of title, who participates in the design, conduct, or reporting of this research, as well as his/her spouse, registered domestic partner, dependents, or other members of his/her household. **The PI is responsible for ensuring that s/he and all other relevant members of the study team review the above questions describing Significant Financial Interests.**

******such as salary, consulting fees, honoraria, or paid authorship

*******through the provision of funds, drugs, devices, or other support for this research

********Such as serving on the Board of Directors or Board of Managers or a position that carries a fiduciary responsibility to the company (e.g., CEO, CFO, CTO, or CMO).

[\[reviewer notes-\]](#)

Supporting Documentation Section

References and Other Attachments

Additional documents:

Name	Modified Date	Version
Data security form	7/26/2016 4:28 PM	0.01
R21 DA042633.pdf	3/11/2016 3:38 PM	0.01
References.pdf	3/11/2016 3:40 PM	0.01

Please use the Add button to the left to upload additional documents if needed.

[\[reviewer notes-\]](#)

ClinicalTrials.gov is a registry and results database of publicly and privately supported clinical studies of human participants conducted around the world.

"[Applicable clinical trials](#)" are required **by federal law** to be registered in [ClinicalTrials.gov](#).

Applicable Clinical Trials (ACTs) are studies that meet the following criteria:

- The study is an interventional study AND
- The study intervention is a drug, biologic, medical device, radiation or genetic AND
- The Study is not Phase 0 or 1 AND
- The study has at least one site in the United States or is conducted under an investigational new drug application or investigational device exemption

NIH Policy

Effective January 18, 2017, revised [NIH](#) Policy requires that all [clinical trials](#) funded in whole or in part by the NIH be registered and results information posted on ClinicalTrials.gov.

As defined by the NIH, a [clinical trial](#) is:

A research study in which one or more human subjects are prospectively assigned to one or more interventions (which may include placebo or other control) to evaluate the effects of those interventions on health related biomedical or behavioral outcomes.

The NIH Policy extends beyond the Food and Drug Administration Amendment Act (FDAAA 801) requirements in that it requires registration and results reporting of:

- clinical trials of behavioral, surgical and other types of health and medical interventions

- phase 1 studies of drugs and biological products
- small feasibility studies of device products

Failure to submit all required registration and results information requested on ClinicalTrials.gov can jeopardize University grant funding, the future funding of the grantee and subject the University of Pittsburgh to future monetary penalties.

In addition, to promote transparency of the clinical trials process, the [International Committee of Medical Journal Editors \(ICMJE\)](#) has established a policy requiring the entry of clinical trials in a public registry, such as ClinicalTrials.gov, prior to subject enrollment as a condition of consideration for publication of the trial results.

*** Based on the above information, will this study be registered in ClinicalTrials.gov?**

Yes

Who will serve as the Responsible Party? UPMC/Pitt Investigator or IND/IDE Pitt Sponsor

Why are you registering your study? (Check all that apply)

It is strongly encouraged by the NIH

If you are not yet registered and need to establish an account for the PI or other research staff that may need to access the record, please send an email to the University of Pittsburgh PRS administrator at [contact] with the following information for each individual:

- Full name
- Telephone number
- Pitt or UPMC email address

If you have any questions or concerns, please email us at [contact].

To find out additional information about how to register your study go to:
<https://www.clinicaltrials.gov/ct2/manage-recs/how-register>
